Population: Our target population is OEF/OIF/OND male and female Veterans eligible for VA care, which we will randomly sample from two overlapping populations. The first group includes those who returned from deployment to Iraq or Afghanistan within the preceding four years and who reside within the catchment areas of one of our 10 study sites (identified by zip code). We want to ensure that those who participate and screen positive on one or more of the screens have access to VA care. Consequently, we have selected the time frame of four years post-deployment because these Veterans have priority access to VA care for five years after their most recent deployment. The second group is OEF/OIF/OND Veterans who are already enrolled in VA care and will not be excluded if they have been home from deployment more than four years. The VA Informatics and Computing Infrastructure (VINCI) provided exact numbers of OEF/OIF/OND Veterans seen at each of our 10 sites: ~238K (202K male/37K female). Overlap will potentially occur among those enrolled in VA care and home from deployment less than four years, therefore we will not stratify sample on this variable, but will take care that the same Veterans [name, sex, age, address] are not sampled twice. Our prior studies have found that approximately half of WEB-ED participants are already VA enrolled, although few have sought MH care. Among those who screened positive on WEB-ED, only 14% had received VA MH care prior to study participation. We do not anticipate any problems recruiting sufficient numbers for our sample as less than 1% of VA users would need to participate to reach our recruitment goals. However, if we need to enhance our recruitment efforts, we will do so by adding additional PBRN-affiliated sites

Sample Identification and Recruitment: We will work with VADIR to obtain contact information and military characteristics for OEF/OIF/OND service members. VADIR is able to provide mailing, phone, and military addresses as well as sociodemographic (e.g.,

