WEB-ED+ augments Current WEB-ED in a next step online interface via Pharos. If successful, this enhancement could be integrated into the next iteration of WEB-ED. Enhanced WEB-ED information and process will be guided and refined by Phase 1 findings as will the preferred means of providing SDM educational YouTube videos and training materials. Enhancements include: **1. An eHealth interface** tailored to Veterans' VA and MHV enrollment needs, links for an electronic interface with VA enrollment, MHV and MHV premium status enrollment, and secure messaging guidance (Appendix 13). **2. A shared decision-making (SDM) interface** Veteran SDM-related educational (e.g., existing YouTube videos) and structured questions about treatment concerns, preferences, and questions and can be accessed through postal and email distribution or Pharos portal. **Provider/TPA SDM** is accessible in the same avenues identified for Veterans. If a TMS training format is preferred, this can be created and accessed the Pharos interface. As presented to key informants in Phase 1, the SDM training models to consider are: 1) The Dartmouth Center for Health Care Delivery Science model that consists of Choice talk, Option talk, and Decision talk about each treatment option and guided by treatment decision aids,⁵⁵ and the AHRQ SHARE approach that encourages SDM processes that include: exploring and comparing the benefits, harms and risks of each treatment option through dialog about what matters most to the patient (Appendices 14-18). These models represent an informed choice model of care as opposed to a paternalistic model focused on the patient in a "sick role."⁵⁶ The University of Iowa (UI) consultants (see [name] and [name] letters), experienced in SDM engagement and training of providers and patients and EMR documentation, will assist us. **The WEB-ED+ Veteran and Provider/TPA SDM interface** (Appendix 19): To return with the informed consent, Veterans will be asked to identify their primary provider. Or, if they are not VA enrolled or have no current provider, the study team will link participants with a TPA at the geographically closest VA. As a minority of Veterans participating in our prior WEB-ED studies have engaged VA MH care, we anticipate this will be a PC provider. If a MH care provider is identified, we will follow the same study process. The Veteran along with their partner provider or TPA will receive information by postal and e-mail outreach by the study team followed by a telephone contact from the Health coach within 10 days of initial outreach. The e-mail will also include a link to a training video that they can access with a unique identification # that will allow them to access a YouTube video about SDM (or TMS type interface). This link is contained in our research network behind the VA firewall which will allow us to determine if the Veteran and Provider/TPA team opened the link and for how long. All **Veterans** will

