
4) Chart review: VA health services utilization will be obtained from VA chart review for all consenting participants. Utilization measures will include: enrollment in VA, MHV enrollment, secure messaging of results, initiation of telephone or face-to-face contact with a provider or TPA interface about screens or secure messaged results, and MH consult sent or services receipt and location (in PC, PCMHI, or MH). We developed an efficient electronic and chart reviewer interface in our CREATE study, which will be leveraged for this study. The VA EMR will be electronically checked monthly for up to 6 months following WEB-ED completion. Chart reviews will encompass VA purchased care records (inclusive of non-VA provider care received via Choice).

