Veteran RCT Recruitment (WEB-ED+) and Assignment: Veterans who screen positive on one or more MH (mental health) screens will be eligible for the RCT and asked online at WEB-ED completion for permission to re-contact them about continuing their participation in the RCT. Those who indicate yes to study re-contact will be sent IRB approved study information, including the RCT consent letter (2B), consent and HIPAA forms attached to this application. Those who decline will be thanked again for their participation and contact will be discontinued. We will use adaptive randomization to achieve balance in the assignment to the treatment intervention arm of WEB-ED+ relative to the control arm of Current WEB-ED. Participants will be sent a letter to inform them about which arm of the RCT they have been assigned to and the expected participation steps for each arm (RCT Intervention Assignment letter or RCT Control Arm Letter). Those who are assigned to the Current WEB-ED arm of the RCT (those who had positive screens for the current WEB-ED, but randomly assigned to no intervention) will not complete Web-Ed+ and will not be contacted until Phase 3. The phase 2D email - RCT will be used to follow up with subjects who have been selected for participation but have not yet completed the additional online screening per randomization.

A medical chart review will be conducted for all subjects who return the signed HIPAA and consent forms for the RCT. Chart reviews will focus on VA care the subject received (or not) including medication, therapy, & any mental health and substance use treatment. We will review the time from post-deployment through 6 months after the subject's initial study participation.

We will assess/confirm enrollment status and upcoming appointments of participating Veterans using a combination of national visual chart review using CAPRI/JLV, along with accessing enrollment and appointment data from the CDW.

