Aim 2 Analyses: We will begin with bivariate analyses (i.e., chi-square test for proportions) to test significance of differences in care engagement between RCT arms. Care engagement is the primary outcome and will be operationalized by VA MH services receipt (yes/no). Our primary analyses will use logistic regression models to estimate the adjusted ORs for treatment engagement controlling for participant characteristics. The logistics regression models will provide an estimate of the association between health care engagement by RCT arm, controlling for covariates such as Veteran gender, prior VA enrollment, severity [screening scores] and complexity [multiple positive screens], patient-activation scores, and rurality. Potential confounding variables that will be assessed in all hypotheses include socio-economic variables (e.g., age, income, marital status), and military characteristics (e.g., months home

from deployment, rank). In addition, depending on the resulting proportions of Veterans who get care in various VA clinics (i.e., PC, PCMH, MH), we plan to conduct a multinomial logistic regression, treating RCT-arm as a covariate. We have used multinomial logistic regression previously to examine associations with three levels of VA health care use (all, some, none).

XI.2

Provide the rationale or power analysis to support the number of subjects proposed to complete this study.

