We will aim for 2000 Veterans completing WEB-ED, with approximately 1100 completing the RCT. Not all 2000 will be eligible for the RCT. Based on our five prior studies, ~77-85% of WEB-ED participants screened positive on at least one of the MH screens (~70% screened positive on depression, PTSD, or substance use). We will assume that 70% will eligible for the RCT (~1400) and use adaptive randomization to assign positive-screener to each RCT arm; two-thirds to WEB-ED+ (~950) and one-third to Current WEB-ED (~450). There are no additional RCT participation activities for those in the Current WEB-ED arm, therefore attrition would be minimal. However, we anticipate there may be attrition among those assigned to WEB-ED+. Our CREATE multi-phase study resulted in attrition of ~30%. Therefore, we expect 650 completers for WEB-ED+. We have increased this sample size to have sufficient power to detect differences per RCT arm. This study is powered to detect whether WEB-ED+ increases VA MH care engagement compared to Current WEB-ED. In our prior work, half indicate that as a direct result of WEB-ED, they will follow up with a provider and 38% with a VA provider, although actual follow-up may be lower (our CREATE study is currently validating participant self-report with chart review data). This proposed study will document VA utilization (including VA purchased care) by VA chart review. We estimated the minimum sample size needed to ensure adequate power (80%) for a variety of assumptions (percentage of Current WEB-ED participants engaging in VA MH care, effect (odds ratios), and variance inflation factors (VIF)57, using nQuery 4.0. We anticipate random assignment will result in no statistical differences between RCT arms based on WEB-ED data (e.g., prior enrollment in VA, positive screens). However, covariates will be included (e.g., gender, rurality, patient-activation scores, VA site) in multivariate analyses to control for variation due to these other variables. Any significant covariates may point to sources of variability to explore in future research efforts, but we do not anticipate having sufficient power to conduct subsample analyses by gender or VA site.

XII. Future Research

XII.1

Do you wish to keep any information about subjects involved with this research project so that members of the current research team may contact them in the future for your own research projects?

Yes

XII.2

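### The primary outcome scores starting and continuing VA MH care alike, so baseline VA MH care should be a named covariate in the primary model

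*Combined protocol and SAP*

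**What the plan says.** **Outcome.** XI.1 (Aim 2 Analyses), repeated in section 4.0, says "Care engagement is the primary outcome and will be operationalized by VA MH services receipt (yes/no"). It does not separate new from continuing care and gives no date from which receipt counts. The chart review item in section 4.0 supplies a follow-up window: "The VA EMR will be electronically checked monthly for up to 6 months following WEB-ED completion".

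**Who can enter.** VII.D.29 says "Veterans who screen positive on one or more MH (mental health) screens will be eligible for the RCT". The Population paragraph of section 4.0 samples two groups: "The second group is OEF/OIF/OND Veterans who are already enrolled in VA care and will not be excluded" for time since deployment. The description of the WEB-ED+ provider interface expects mostly primary care providers to be named, but adds "If a MH care provider is identified, we will follow the same study process". No visible text excludes Veterans already in VA MH care.

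**Covariates.** XI.1 fits the logistic model "controlling for covariates such as Veteran gender, prior VA enrollment, severity [screening scores] and complexity [multiple positive screens], patient-activation scores, and rurality", and will also assess socio-economic and military variables as confounders. XI.2 says "covariates will be included (e.g., gender, rurality, patient-activation scores, VA site"). Baseline VA MH care appears in none of these lists.

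**What is collected.** The pre-intervention survey (section 4.0 and VII.E.6) asks about past and present MH use inside and outside VA. The chart review (VII.D.29 and VII.E.6) reaches back to the end of deployment and runs to 6 months after study entry.

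**Earlier studies.** "Among those who screened positive on WEB-ED, only 14% had received VA MH care prior to study participation", while about half of participants were VA enrolled (section 4.0, Population).

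**The concern.** The trial's rationale is unmet need, but the outcome cannot tell whether WEB-ED+ brought Veterans into MH care or whether care already under way carried on. A Veteran who keeps a routine MH appointment is a success in either arm. The engagement rates and the odds ratio therefore mix two different things, and the visible text plans no arm comparison by baseline MH care.

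The second cost is precision. Someone already in care is far more likely to be seen again, so baseline care should explain a good deal of the outcome variation. Prior VA enrolment is named, but it is a weak stand-in: roughly half were enrolled against 14% with prior VA MH care, so most enrolled Veterans would have had no such care.

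**Working it through.** **Inputs from the documents.** Prior VA MH care among screen-positives 14% (Population). Control engagement 25%, 30% or 35% and OR 1.5 (power table, section 4.0). Analysed numbers 450 Current WEB-ED and 650 WEB-ED+ (XI.2).

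**Assumptions.** The share *c* of prior users seen again within 6 months is not given, so 40, 60, 80 and 90% are tried. Alpha and sidedness are not stated, so two-sided 0.05 is used, with one-sided 0.05 alongside.

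**The plan's own figure.** For OR 1.5 at 25%, the WEB-ED+ rate is 0.375/1.125 = 0.333. The two-proportion formula with 2:1 allocation, 80% power and one-sided 0.05 gives 278 controls, and 278 × 3 = 834, the tabulated total. The same formula matches eight of the nine cells without variance inflation, so the one-sided results below are closest to the plan's calculation.

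**Step 1: continuing users among control-arm engaged cases.** Share = 0.14*c* / control rate.
- At 25%: 0.056, 0.084, 0.112 and 0.126 over 0.25 = 22, 34, 45 and 50%.
- At 35%: the same numerators over 0.35 = 16, 24, 32 and 36%.

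**Step 2: power from adding baseline care, uniform effect.** The rate in Veterans without prior care is (0.25 − 0.14*c*)/0.86, for example 0.160 at *c* = 80%. Simulation: 20,000 trials per scenario, 50% enrolled, prior users nested within the enrolled, marginal OR 1.5, Wald test, two-sided.

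| *c* | Enrolment-adjusted | Plus baseline care | Gain (points) | Restricted to no prior care |
|---|---|---|---|---|
| 40% | 85.2% | 85.7% | 0.5 | 78.3% |
| 60% | 85.4% | 88.5% | 3.1 | 81.6% |
| 80% | 86.3% | 92.8% | 6.5 | 89.3% |
| 90% | 86.6% | 95.0% | 8.4 | 93.4% |

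The gain is about 0–5 points one-sided, and 0–4 points two-sided with 7% prior users. At a 35% control rate, an expected-data calculation without enrolment in the model gives about 0–5 points two-sided and 0–3 one-sided. Rejection under OR 1.0 was 4.7–5.1% in every simulated model.

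**Step 3: effect only in Veterans without prior care (OR 1.5), 25% control rate.** At *c* = 80%, their rate moves from 0.160 to 0.223. The WEB-ED+ total is 0.112 + 0.86 × 0.223 = 0.304, a whole-sample OR of 1.31. Across the four values of *c* (40, 60, 80, 90%):
- Whole-sample OR: 1.40, 1.36, 1.31, 1.28.
- Power, enrolment-adjusted: 68.2, 60.3, 51.0, 45.6%.
- Power, plus baseline care: 68.5, 63.1, 59.5, 58.5%.
- Power, restricted to no prior care: 76.4, 72.2, 66.2, 62.7%.

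The restricted comparison does better here and worse in Step 2, so it belongs among the supportive results.

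**Step 4: dates.** Records are followed from WEB-ED completion, but VII.D.29 and VII.E.6 place mailed consent between that point and assignment. Care received in the gap cannot be caused by the arm. Illustration: suppose 20% of control events (0.05) fall in the gap. The remaining rate is 0.20/0.95 = 0.211, which OR 1.5 raises to 0.286. The WEB-ED+ total is 0.05 + 0.95 × 0.286 = 0.321, an OR of 1.42. With 10% and 30% in the gap, the OR is 1.46 and 1.38. The size of the gap is an assumption.

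**The case against.** **Including current users may be deliberate.** Enrolled Veterans are a sampling target, and those with an MH provider follow the same process, so improving existing care is within scope. This stands. A reader might infer an eligibility error, but the documents do not support that.

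**The covariate lists are open.** Both give examples only, and XI.1 refers generally to participant characteristics. This also stands: baseline MH care is unnamed, not ruled out. The chart review template is an attachment that cannot be seen and might record it. Neither fact commits the primary model to using it.

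**Randomisation prevents bias.** It does so when everyone randomised is analysed, so omitting the covariate does not bias that comparison. The protection does not extend to the 450 versus 650 used for power, which are completer counts after about 30% attrition in WEB-ED+ only.

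**The gain may be trivial.** At 40% seen again it is about half a point. The 14% is any prior care, and care within a fixed recent period cannot exceed that share in the same population. Deliberate sampling of enrolled Veterans could push it the other way. At a marginal OR of 1.5, power without the covariate is already 85–87%, so the documents do not support reading this point as showing an underpowered trial.

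**Contact about the screens is already measured.** Section 4.0 lists starting such contact as a utilisation measure, but XI.1 does not make it the primary outcome.

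**Conclusion.** The point holds as an improvement to the specification, not as an error. The outcome pools starting with continuing care, and a probable strong predictor that is already collected is not committed to the primary model. On the stated assumptions, continuing users are 22–50% of control-arm engaged cases at a 25% control rate and 16–36% at 35%. The covariate adds about 0–8 and 0–5 points of two-sided power respectively, and less one-sided or with fewer prior users. These ranges rest mainly on the unsourced 40–90% return rate and on carrying 14% over from earlier studies. The problem of interpretation remains at any of these values. Priority is modest.

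**What to change.** Keep the primary outcome and the population.

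1. Require VA MH care (yes/no, from chart review) in a fixed look-back before WEB-ED completion, for example 12 months, as a covariate in the primary logistic model. State that care before WEB-ED completion never counts toward the outcome. The look-back and the outcome window must meet at one date and not overlap.
2. Add a sensitivity analysis in which the look-back ends, and outcome counting starts, at the assignment date. This removes care received in the consent gap.
3. As supportive results, report engagement by arm split by baseline VA MH care, and the arm comparison among Veterans without it.
4. Analyse everyone randomised, in the arm assigned.

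**Cost.** One degree of freedom and a little extra analysis, with no new data collection. The restricted comparison uses about 86% of the sample if 14% are prior users. The enrolment history lists enrolment as stopped at the 02/29/24 review, and subjects are not blinded (VII.E.1.a), so each addition should carry the date it was made.

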 We are modifying to add the final educational documents that will be used in the study.	Miscellaneous	2	19 k	E	02/07/22
Bad Contact Info Call Script and Email.docx	Miscellaneous	1	25 k	E	12/16/22
CHART REVIEW 12-14-22.docx	Miscellaneous	2	14 k	E	01/14/21
CONTACT INFORMATION FORM - Veterans.docx	Miscellaneous	4	16 k	E	07/16/19
CONTACT INFORMATION FORM.docx	Miscellaneous	1	36 k	E	08/10/17
Crisis Call Procedures-Steps for Managing Crisis Calls + Warm Transfers to VCL 2015.03.docx	Miscellaneous	4	155 k	E	05/27/21
Depression Educational Module updated links 4.20.21.pdf	Miscellaneous	2	1 M	E	07/12/21
 This change is to remove broken web links and add current web links.	Miscellaneous	4	17 k	E	07/12/21
Encrypted email notice to Veteran.rtf	Miscellaneous	1	362 k	E	07/02/20
FAQ_eSDM Qualtrics.docx	Miscellaneous	1	358 k	E	07/02/20
FINAL Decision Aid-AUD.pdf	Miscellaneous	1	319 k	E	07/02/20
 We are modifying to add the final decision aid documents that will be used in the study.	Miscellaneous	1	17 k	E	12/14/22
FINAL Decision Aid-Depression.pdf	Miscellaneous	1	121 k	E	07/02/20
 We are modifying to add the final decision aid documents that will be used in the study.					
FINAL Decision Aid-PTSD.pdf					
 We are modifying to add the final decision aid documents that will be used in the study.					
Follow up script with RCT new reimbursement.docx					
Insomnia Educational Module.pdf					

█ We are modifying to add the final educational documents that will be used in the study.	Miscellaneous	5	27 k	E	04/03/19
Interview Sign In Sheet (1).doc	Miscellaneous	3	132 k	E	07/02/20
█ We are modifying to add the final educational documents that will be used in the study.	Miscellaneous	1	213 k	E	06/26/19
LMR SIGNED CONCURRENCE -- BY [name] 00240542 19-C-85212 LMR Concurrence signed Online and Shared Decision Making Interventions for Post-Dep.pdf	Miscellaneous	3	37 k	E	03/16/20
Link Email AGS Final 03_16_2020.docx	Miscellaneous	1	243 k	E	07/02/20
█ We are modifying to add the final educational documents that will be used in the study.	Miscellaneous	1	729 k	E	08/10/17
MHV Linkage Enrollment Flowchart.pdf	Miscellaneous	3	185 k	E	07/02/20
█ We are modifying to add the final educational documents that will be used in the study.	Miscellaneous	1	24 k	E	04/05/22
Missing_email_notice_to_treatment_arm_RCT_participants.docx	Miscellaneous	1	19 k	E	01/21/20
NON SDM 121919.docx	Miscellaneous	1	35 k	E	03/06/19
Phase 1 Confirmation Email.docx	Miscellaneous	1	72 k	E	03/06/19
Phase 1 Leadership Thank You Letter.docx	Miscellaneous	1	12 k	E	03/06/19
Phase 1 Web Link_Mailed Scheduling Template.docx	Miscellaneous	1	72 k	E	03/06/19
Phase 1G Key Expert Thank You Letter.docx	Miscellaneous	4	1 M	E	09/13/21
Phase 2 RCT missing VA enrollment reminder.rtf	Miscellaneous	2	24 k	E	12/19/22
Phase 2 New RCT Reimbursement email notification.docx	Miscellaneous	1	21 k	E	12/14/22
Phase 2 New Reimbursement postal mail.docx	Miscellaneous	3	1 M	E	09/09/21
█ Information was added to assist Veterans with enrolling in My HealtheVet secure electronic health record system.	Miscellaneous	4	112 k	E	08/11/22
Phase 2 RCT Provider Instructions Email.rtf	Miscellaneous	4	1 M	E	09/13/21
Phase 2 RCT missing secure messaging reminder.rtf	Miscellaneous	4	247 k	E	12/19/22
Phase 2 Thank you letter-returned forms.rtf	Miscellaneous	2	54 k	E	07/12/21
Phase 2G Incomplete Survey Email.docx	Miscellaneous	2	53 k	E	07/12/21
Phase 2H Incomplete Survey Letter.docx	Miscellaneous	5	1 M	E	07/12/21
Phase 2I Thank you letter.rtf	Miscellaneous	2	1 M	E	05/28/21
█ Editing changes were made to provide consistent information as given in other documents used in this study and improve readability for the study participants.	Miscellaneous	1	494 k	E	08/10/17
Post Traumatic Stress Disorder.pdf	Miscellaneous	3	113 k	E	07/02/20
█ We are modifying to add the final educational documents that will be used in the study.	Miscellaneous	4	175 k	E	05/27/21
Postdeployment Family Adjustment Educational Module updated links 5.11.21.pdf	Miscellaneous	3	89 k	E	07/02/20
█ This change was to remove broken web links. Current web links were added.	Miscellaneous	1	39 k	E	08/10/17
Prescription Drug Misuse Educational Module.pdf	Miscellaneous	1	16 k	E	04/05/22
█ We are modifying to add the final educational documents that will be used in the study.	Miscellaneous	3	15 k	E	10/05/21
Provider Info Sheet to be completed by Veteran.docx	Miscellaneous	1	109 k	E	09/09/21
RCT Control Arm letter.rtf	Miscellaneous	3	187 k	E	12/19/22
█ This letter informs the Veteran which arm of the study group they have been randomly assigned to and what to expect	Miscellaneous	1	18 k	E	11/01/22
RCT Intervention Assignment Letter.rtf	Miscellaneous	23	66 k	E	12/19/22
REF 10-22 eSDM Summary Report Error Email Notification.docx	Miscellaneous	3	36 k	E	05/13/22
█ This is the email to be sent notifying subjects of the incorrect blank template that they received in error. This document was also included as an attachment in the reportable event form.	Miscellaneous	1	20 k	E	02/07/22
Recruitment Scripts.docx	Miscellaneous	1	14 k	E	01/21/20
Reimbursement Follow-up Email_Revised - Final.docx	Miscellaneous	1	13 k	E	01/21/20
Requested Resources Email Scripts.docx	Miscellaneous	1	120 k	E	06/26/19
SDM Provider Animation 121919.docx	Miscellaneous	1	90 k	E	08/10/17
SDM Veteran animation 121919.docx	Miscellaneous	1	169 k	E	08/10/17
[name] HSRD HX002185-01A2- Union Information with interview questions.pdf	Miscellaneous	4	103 k	E	10/25/21
Sample_WEB_ED_Neg_Screen.pdf	Miscellaneous	1	14 k	E	06/26/19
Sample_WEB_ED_Pos_Screen.pdf	Miscellaneous	1	250 k	E	07/02/20
Screening Summary - Secure Message.rtf	Miscellaneous	7	87 k	E	12/19/22
Skype Script.docx	Miscellaneous	3	151 k	E	07/02/20
█ We are modifying to add the final educational documents that will be used in the study.	Miscellaneous	1	20 k	E	02/07/22
Social Determinants of Health Educational Module.pdf	Miscellaneous	1	20 k	E	02/07/22
█ We are modifying to add the final educational documents that will be used in the study.	Miscellaneous	1	20 k	E	02/07/22
Study_Q&A - Current Web-Ed.rtf	Miscellaneous	1	20 k	E	02/07/22
Substance & Alcohol Misuse Educational Module.pdf	Miscellaneous	1	20 k	E	02/07/22
█ We are modifying to add the final educational documents that will be used in the study.	Miscellaneous	1	20 k	E	02/07/22

Suicide Prevention Educational Module.pdf	Miscellaneous	1	158 k	E	07/02/20
☒ We are modifying to add the final educational documents that will be used in the study.					
To share with Provider.rtf	Miscellaneous	1	65 k	E	07/22/21
☒ This form will enable the Veteran to indicate which screening results they are most concerned about and would like to discuss with their health care provider.					
Traumatic Brain Injury Educational Module updated links 4.20.21.pdf	Miscellaneous	5	160 k	E	05/27/21
☒ This change was to remove broken web links and add active links to online information.					
VA10091 05.22.17.pdf	Miscellaneous	1	811 k	E	08/10/17
assurance-document.pdf	Assurance Document	1	39 k	E	08/09/17
